## 2 PROJECT OBJECTIVES AND DESIGN

### 2.1 Hypothesis and primary objective

Hypothesis: It is hypothesized that advanced subject-specific musculoskeletal modelling in combination with mobile monitoring technology as embedded in the iPhone and Apple Watch allow for accurate prediction of changes in muscle strength and muscle size in the lower limbs following an 8-week strength training intervention of key muscle-tendon groups associated with knee joint stability.

Primary Objective: Prediction of changes in muscle strength in the lower limbs due to different strength training volumes by means of the advanced computational modelling, biomechanical analysis and mobile monitoring technology. Of particular interest is the prediction of 1RM and the prediction of the ratio between hamstrings and quadriceps strength (H:Q ratio) compared against isokinetic strength tests as gold standard. Research has clearly shown that the quantification of 1RM is fundamentally important when it comes to the design of safe and efficient resistance training programs. Improved accuracy in the 1RM prediction compared to preliminary studies (i.e. mean %error of 0.27% in 60% and 7.81% in 80% 1RM assessment [29-34]) is expected through the consideration of data from optical motion capture as well as the additional consideration of subject-specific musculoskeletal anatomy from computational modelling.

Secondary Objective: Assessment of changes in muscle size in the lower limbs due to different strength training volumes using the HMF technique. Of particular interest is the prediction of muscle volume using the HMF technique compared against data from MRI as gold standard, as well as the prediction of adaptation in hamstrings and quadriceps CSA due to the strength training intervention using HMF versus data from ultrasound, respectively. Improved accuracies in the assessment of muscle size compared to preliminary studies (i.e. more than 70% accuracy in muscle volume [22]) are expected through the additional data from anthropometric measurements and the matching of generic model to the study-specific population group including gender.

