### 2.2 Primary and secondary endpoints

Primary Endpoint: Changes in muscle strength in the lower limbs following the 8-week strength training intervention of the lower limbs in three study groups with different training volumes. The two strength-specific primary outcome parameters are: 1RM and H:Q ratio. Changes in 1RM and H:Q ratio will be derived using the *iOS Strength Control app* and biomechanical analysis before and after the strength training intervention. Primary outcome parameters will be compared between the three study groups in relation to training volumes (Group#1: no training, Group#2: 1 training per week, Group#3: 3 trainings per week). The accuracy in the prediction of 1RM and H:Q ratio will be compared with data from isokinetic strength tests as gold standard.

Secondary Endpoint: Changes in muscle size of the lower limbs following the 8-week strength training intervention of the lower limbs in three study groups with different training volumes. The two secondary outcome parameters are: muscle volume and CSA. Changes in muscle volume and CSA will be derived using the HMF technique in combination with data from 3D body surface scanning and anthropometric measurements before and after the strength training intervention. Secondary outcome parameters will be compared between the three study groups in relation to training volumes (Group#1: no training, Group#2: 1 training per week, Group#3: 3 trainings per week). The accuracy in the derivation of muscle volume and CSA using the HMF technique will be assessed using data from MRI and ultrasound as gold standard.

Key baseline factors that will likely influence the primary and secondary endpoints are strength training experience and gender. The sample size and population group are specified to allow the analysis of gender-specific differences on study results. Thereby, the inclusion/exclusion criteria and study protocol, including a training-related questionnaire, are defined to minimize the bias of training experience.

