## 4 STATISTICS AND METHODOLOGY

### 4.1. Statistical analysis plan

Statistical analysis will be conducted with SPSS (SPSS v. 21, IBM, USA) after consultation with a statistician in line with previous research by our group.

For the Primary Objective, a repeated measures analysis of variance (ANOVA) will be conducted to assess statistically significant differences between the predicted values of 1RM and H:Q ratio from biomechanical modelling and mobile monitoring with the measured values from optical motion capture and isokinetic strength tests following the 8-week strength training intervention. A correlation analysis will be done to relate the strength-specific outcome parameters to the training-specific parameters for each study group. Principal component and factor analysis will be performed to identify correlations between strength-specific and training-specific parameters.

For validation of the HMF technique, we will follow the statistical methods of previous research by our group [21, 22] to assess the significance in the differences of muscle volume between HMF and MRI, as well as the difference of the predicted adaptation in CSA between HMF and ultrasound. The level of significance in the difference of muscle volume between HMF and MRI is expected to vary across muscle-tendon groups and gender. In particular, no significant differences were found in the predicted volume of semitendinosus and semimembranosus as part of the hamstrings between HMF and MRI in 5 children without CP (MRI 5.1 (0.91) versus HMF 5.0 (0.30) cm^3/kg, p-value >0.05) and in the predicted volume of the quadriceps, including vastus lateralis, medialis, intermedius and rectus femoris, in 6 children with CP (MRI 15.9 (3.20) versus

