HMF 16.5 (2.58) cm^3/kg, p-value > 0.05), respectively [22]. It is expected that the accuracy in the predicted muscle volume is improved in the present study by fitting a generic musculoskeletal model to subjects of similar age and gender, and without significant musculoskeletal impairments, as well as additionally considering subject-specific somatotype based on anthropometric measurements. ANOVA will be performed to analyse the pairwise differences in muscle volumes between the HMF and MRI-based results; and to analyse the pairwise differences in the predicted adaptation of hamstrings and quadriceps CSA between HMF and data from ultrasound before and after strength training intervention, respectively. The data from female and male participants will be analysed combined, as well as independently as two different groups.

The level of significance will be set at  $p < 0.05$  for all statistical tests.

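### Section 4.1 tests mean differences at p < 0.05 and sets no agreement measure or margin, although the hypothesis is accurate prediction of changes

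*Combined protocol and SAP*

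**What the plan says.** Section 2.1 hypothesises that the modelling and mobile monitoring "allow for accurate prediction of changes in muscle strength and muscle size in the lower limbs following an 8-week strength training intervention". Section 2.2 adds, for the primary outcome parameters: "The accuracy in the prediction of 1RM and H:Q ratio will be compared with data from isokinetic strength tests as gold standard". Section 1.4 puts the key research question as one of how accurately changes can be predicted.

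Section 4.1 then specifies these analyses:

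- **Strength:** "a repeated measures analysis of variance (ANOVA) will be conducted to assess statistically significant differences between the predicted values of 1RM and H:Q ratio" and the values measured by optical motion capture and isokinetic tests.
- **Muscle size:** "ANOVA will be performed to analyse the pairwise differences in muscle volumes between the HMF and MRI-based results", and likewise for the predicted adaptation in cross-sectional area (CSA) against ultrasound.
- **Other analyses:** "A correlation analysis will be done to relate the strength-specific outcome parameters to the training-specific parameters for each study group". Principal component and factor analysis serve the same purpose. None of these sets prediction against measurement.
- **Criterion:** "The level of significance will be set at $p < 0.05$ for all statistical tests".

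As supporting evidence, sections 3.1 and 4.1 report that "no significant differences were found in the predicted volume of semitendinosus and semimembranosus as part of the hamstrings between HMF and MRI"; the sample there was five children who did not have cerebral palsy. Both sections make a similar statement for the quadriceps in 6 children with cerebral palsy.

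**The concern.** How accurate a prediction is depends on its systematic error and on the scatter of its individual errors. A test of mean difference asks only whether the average error is distinguishable from zero. Over- and under-predictions cancel in that average, and scatter enters only as noise that makes the test less likely to reject. A non-significant result can therefore mean good agreement, large random error or too few participants, and the p-value does not say which.

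Section 2.3 calls the study confirmatory. If p < 0.05 remains the only stated criterion, the main conclusion about the technology will rest on a statistic that does not measure what the hypothesis asserts. Group or time terms in the repeated measures model would not change this, because they too compare means.

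**Working it through.** **Inputs from the documents**

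- Section 4.2: 36 complete datasets for the primary endpoint, 12 for the secondary. Section 2.3: 18 women and 18 men overall, 6 and 6 in the MRI sub-group. Section 4.1: the sexes are analysed combined and separately, so n is 36 and 18 for strength, 12 and 6 for MRI.
- Section 4.1: significance at 0.05. Sidedness is not stated; I assume two-sided.
- Sections 3.1 and 4.1, earlier HMF work (mean and SD, cm³/kg): hamstrings MRI 5.1 (0.91), HMF 5.0 (0.30), n=5; quadriceps MRI 15.9 (3.20), HMF 16.5 (2.58), n=6.

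**1. The plan's sample size.** The effect size reproduces: (200.8 − 170.6)/√((21.4² + 19.0²)/2) = 30.2/20.2 = 1.49, stated as 1.5. Eleven per group also reproduces for two independent means at one-sided 0.025 (power 0.917). The calculation is sound in that form, but it concerns a change in 1RM and says nothing about agreement.

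**2. What the planned test responds to.** For paired values t = √n × (mean difference)/(SD of differences), so the result is significant when |mean difference|/SD exceeds t(0.975; n−1)/√n:

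| n | t | critical \|bias\|/SD |
|---|---|---|
| 36 | 2.030 | 0.34 |
| 18 | 2.110 | 0.50 |
| 12 | 2.201 | 0.64 |
| 6 | 2.571 | 1.05 |

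The smallest subgroup needs the largest relative bias before a difference is declared.

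**3. Illustration by noncentral t.** The error sizes are assumptions, not document figures.

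- Offset 2%, SD 3% (ratio 0.67), n=36: significant in 97% of trials. Limits of agreement are 2 ± 1.96 × 3, or −3.9% to +7.9%. A repeated measures main effect with three groups (33 df) also gives 97%.
- Bias 15%, SD 30% (ratio 0.5): non-significant in 65% at n=12 and 83% at n=6. Limits are 15 ± 1.96 × 30, or −43.8% to +73.8%.

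The first prediction is far closer to the truth, yet it is the one more likely to be flagged as different. An offset below about 0.34 SD would usually not be flagged at n=36. Any unbiased method is non-significant in 95% of trials whatever its SD; that follows from alpha alone.

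**4. The documents' own examples.** SD of differences = √(s₁² + s₂² − 2r·s₁·s₂). The between-method correlation r is not given; I take 0 to 0.9. Percentages are of the average of the two methods' means (5.05 and 16.2).

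| Muscle group | r | SD of differences | p | 1.96 × SD | % of mean |
|---|---|---|---|---|---|
| Hamstrings, n=5 | 0 | 0.96 | 0.83 | ±1.88 | ±37% |
| Hamstrings, n=5 | 0.9 | 0.65 | 0.75 | ±1.28 | ±25% |
| Quadriceps, n=6 | 0 | 4.11 | 0.74 | ±8.06 | ±50% |
| Quadriceps, n=6 | 0.9 | 1.43 | 0.35 | ±2.80 | ±17% |

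The reported p > 0.05 reproduces in every row, whether the limits are ±17% or ±50%. The p-value does not separate these cases.

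**The case against.** The strongest reply is that the plan never makes p > 0.05 the accuracy criterion. A reader might infer a rule under which a noisy method passes and a precise one fails. No sentence states such a rule, and it should not be attributed to the sponsor. What stands is that p < 0.05 is the only criterion given, and that non-significance in 5 and 6 children is offered as support.

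Second, a reader might conclude that the study cannot say how accurate the prediction is. That goes too far. Section 2.1 frames success as improving on error figures (mean error 0.27% and 7.81% for 1RM, more than 70% accuracy for volume). Section 4.1 follows earlier methods for HMF, and section 1.2 says that earlier work reported average errors (under 10% for length, under 30% for volume). Error summaries may therefore be intended for HMF; this cannot be checked from the documents. The stated aim of that sentence is still the significance of differences. The 1RM and H:Q comparison has no such cover beyond a general phrase about consistency with the group's previous research.

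Third, the hamstring SDs (0.30 against 0.91, ratio 0.33) might suggest that HMF captures only a third of the spread between subjects. With n=5, and treating the two SDs as independent, the 95% interval for that ratio is about 0.11 to 1.02. The quadriceps ratio is 2.58/3.20 = 0.81. Neither example settles the matter.

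**Conclusion.** The concern holds in this form: the comparisons of predicted with reference values that section 4.1 spells out test mean differences, and no agreement measure or accuracy margin is prespecified for a hypothesis about accuracy. It matters most for 1RM and H:Q ratio, which carry the primary objective. For HMF it is tempered by the reference to earlier methods.

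The critical ratios (0.34, 0.64 and 1.05 at n=36, 12 and 6) follow from the planned numbers and a two-sided 0.05 level. The 97%, 65% and 83% figures rest on assumed errors and show direction, not expected performance. The limits of agreement for the earlier examples (±25% to 37% for hamstrings, ±17% to 50% for quadriceps) rest on an assumed correlation of 0 to 0.9 and on very small samples. They show that a non-significant difference is compatible with wide individual error; they do not show that HMF is inaccurate.

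**What to change.** In section 4.1, make agreement the primary accuracy analysis. The ANOVA may stay as a secondary analysis. Report mean bias with 95% CI, 95% limits of agreement with CIs, and mean absolute (unsigned) percentage error for:

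- H:Q ratio against the isokinetic test;
- 1RM against a reference value on the same scale, stating which;
- HMF muscle volume against MRI, at baseline only;
- HMF CSA against ultrasound.

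For H:Q ratio, 1RM and CSA, do this for single-visit values and for pre-post change. Section 4.1 already compares CSA adaptation, so that part only needs the new statistics. MRI is done once, at baseline, so predicted change in volume cannot be validated against it; the plan should say so.

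Set an accuracy margin for each outcome before analysis, and claim accuracy only if both the CI of the bias and the limits of agreement meet it. The figures of 7.81% (section 2.1) and under 30% (section 1.2) are average errors. They can serve as comparators for mean error, but not as ready-made margins for individual limits.

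The change needs no new measurements. Its costs are that margins must be chosen in advance, the method may fail them, and precision is limited. The 95% CI half-width of each limit is t × √(1/n + 1.96²/(2(n−1))) SDs: about 0.58 at n=36, 1.12 at n=12 and 1.9 at n=6. MRI and by-sex results should therefore be reported as estimates.

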The MRI-based assessment of muscle volume for validation of the HMF technique is analyzed independently from the strength training intervention. Thereby, the accuracy of the HMF technique is dependent on the initial generic musculoskeletal model that is used for model fitting, as well as the available subject-specific skin surface and anthropometric data. The level of significance in the difference of muscle volume between HMF and MRI is expected to vary across muscle-tendon groups, as well as between population groups and gender. In particular, no significant differences were found in the predicted volume of semitendinosus and semimembranosus as part of the hamstrings between HMF and MRI in 5 children without CP (MRI 5.1 (0.91) versus HMF 5.0 (0.30)  $\text{cm}^3/\text{kg}$ ,  $p\text{-value} > 0.05$ ) and in the predicted volume of the quadriceps, including vastus lateralis, medialis, intermedius and rectus femoris, in 6 children with CP (MRI 15.9 (3.20) versus HMF 16.5 (2.58)  $\text{cm}^3/\text{kg}$ ,  $p\text{-value} > 0.05$ ), respectively [22]. Based on previous research, it can be expected that additional consideration of somatotype from anthropometric measurements will help to improve model fit by allowing to adjust the relative thickness of the skin layer, and thus segmental inertia properties, via the HMF objective function for individual subjects. Furthermore, it is very likely that the accuracy in fitting results will be improved when fitting a generic musculoskeletal model to subjects of similar age and gender, and without significant musculoskeletal impairments, which will be the case in the present study. Further details to the MRI-based analysis are provided in Subsection 3.3.

All participants have to confirm their voluntary participation with a written informed consent before being submitted to any study procedure.

Inclusion criteria (all participants,  $n=36$ ):

- Healthy participants; and
- Age 18-40 years old; and
- No acute or chronic musculoskeletal symptoms or pain; and
- Experience with strength training (at least 1-year strength training experience with one training session per week or more); and
- Familiar with strength exercises of key muscles associated with knee joint stability.

Exclusion criteria (all participants,  $n=36$ ):

- Acute or chronic musculoskeletal pain; and/or
- Musculoskeletal surgery within the last 12 months; and/or
- Ongoing rehabilitation or treatment of musculoskeletal complaints or injury; and/or

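### The analyses of prediction accuracy in section 4.1 name no training-group factor, so errors that run in opposite directions in the low- and high-volume groups can cancel

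*Combined protocol and SAP*

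**What the plan says.** Section 4.1 plans two kinds of predicted-versus-reference analysis that bear on the intervention.

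- **Strength.** The sentence on accuracy reads: "a repeated measures analysis of variance (ANOVA) will be conducted to assess statistically significant differences between the predicted values of 1RM and H:Q ratio". The comparator is what is measured once training has ended. No between-subject factor is named.
- **Muscle size.** An ANOVA is planned, and its subject is stated as "pairwise differences in the predicted adaptation of hamstrings and quadriceps CSA between HMF and data from ultrasound before and after strength training intervention". The HMF paragraph closes with the only stratification in the section: "The data from female and male participants will be analysed combined, as well as independently as two different groups".

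Training group does appear elsewhere, but not in relation to error against the reference.

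- Section 4.1: "A correlation analysis will be done to relate the strength-specific outcome parameters to the training-specific parameters for each study group". This relates outcomes to training parameters, not predicted to measured change.
- Section 2.2: "Primary outcome parameters will be compared between the three study groups in relation to training volumes", and likewise "Secondary outcome parameters will be compared between the three study groups in relation to training volumes". These compare the predicted or HMF-derived outcomes themselves.
- Section 2.2 on accuracy: "The accuracy in the derivation of muscle volume and CSA using the HMF technique will be assessed using data from MRI and ultrasound". It says nothing about doing this by group.

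Allocation is random to no, one or three sessions a week, 12 per group with 6 women and 6 men in each (section 3.3). No numerical accuracy criterion is given.

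**The concern.** The randomised groups exist to produce different true changes. A method that predicts change from training volume must get the size of change right at each volume, and the three groups are where this can be tested. The written accuracy analyses average over that contrast.

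A method that pulls its predictions toward the overall average will predict too much change in Group#1 and too little in Group#3. In a pooled mean difference these errors offset each other. Splitting by sex does not help: each sex is spread evenly over the three groups, so the same cancellation occurs within women and within men if their average changes are similar. The trial could then report no significant difference between predicted and reference change without having tested whether the method follows training volume, which is the question in section 1.4.

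**Working it through.** **Inputs from section 3.1.** Squat 1RM in the cited study was 170.6 ± 21.4 kg before and 200.8 ± 19.0 kg after training; d = 1.5, alpha 0.025, power 0.9, 11 per group required, 12 planned.

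**The plan's own figures.**
- Gain: 200.8 − 170.6 = 30.2 kg.
- Pooled SD of levels: √((21.4² + 19.0²)/2) = 20.2 kg.
- d = 30.2/20.2 = 1.5, as stated.
- A two-sample t-test with d = 1.5, one-sided alpha 0.025 and power 0.9 gives 10.40, so 11 per group, as stated. Two-sided 0.025 would give 12.39, so 13.

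**Assumptions added here, because the documents give no group-specific changes and no SD of prediction error.** True mean gains are 0, 15.1 (= 30.2/2) and 30.2 kg in Groups 1 to 3. The SD of the error of change is 20.2 kg, borrowed from the SD of 1RM levels, with 15 to 30 kg as a range. Tests are two-sided at 0.05.

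**Why the pooled mean is blind.** Let a method predict average + k × (true − average), with average 15.1 kg. The mean error in a group is (k − 1) × (true − average).
- k = 1 (correct): 0, 0, 0.
- k = 0.5: +7.55, 0, −7.55 kg; mean 0.
- k = 0 (15.1 kg for all): +15.1, 0, −15.1 kg; mean 0.

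The pooled mean error is zero for every k.

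**Chance of flagging the k = 0 method.** The pooled test is a one-sample t-test on 36 errors, equivalent to the two-level method effect in a repeated measures ANOVA of change. The method-by-group term is a one-way ANOVA of the errors, with effect size f = √((15.1² + 0² + 15.1²)/3)/SD = 12.33/SD.

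| Error SD (kg) | f | Method-by-group term flags |
|---|---|---|
| 15 | 0.82 | 99% |
| 20.2 | 0.61 | 89% |
| 25 | 0.49 | 72% |
| 30 | 0.41 | 55% |

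At SD 20.2 kg, the pooled test flags the method in about 2% of 20,000 simulated trials. By sex it is 2.3% in women and 2.4% in men, with equal mean change assumed. These rates are below 5% because the spread between groups inflates the error SD used by the test. A t-test within Group#1 or Group#3 alone flags it in about 65%.

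**Wider range, in SD units.** With a top-group change of 0.5 to 1.5 and an SD of change of 0.5 to 1, the pooled test flags the centred constant in 0.2% to 4.8% of trials and the method-by-group term in 17% to about 100%.

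**Constants that are not centred (base case).** If the common prediction is off the average by 0.25 SD, the pooled test flags it in 20% of trials; by 0.5 SD, 73%; by 0.75 SD (for example, no change predicted for anyone), 98%.

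**Precision by group.** With 12 participants and SD 20.2 kg, the 95% CI half-width of a group mean error is 2.20 × 20.2/√12 = 12.8 kg.

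**The case against.** Several objections have force.

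- **Not every uniform prediction escapes.** A reader might infer that any method giving everyone the same change would pass. The off-centre figures above show otherwise; cancellation needs predictions centred on the average change.
- **Shrinkage toward zero is a different case.** The pilot SDs for hamstring volume (0.30 for HMF, 0.91 for MRI) might suggest that HMF captures only a third of true change. The documents do not support this. The figures are volumes, not changes, in five children, and the quadriceps figures quoted beside them give 2.58/3.20 = 0.81. Such errors also share a sign. With predictions shrunk to 0.33 of the true gain, the pooled test flags about 78% of trials and the group term about 54% (SD 20.2 kg). The pooled test should therefore stay.
- **Section 2.2 is a partial safeguard.** A constant prediction would show no difference between groups. But the comparison is not tied to the reference. At k = 0.5 the predicted Group#3 minus Group#1 difference is 15.1 kg against a true 30.2 kg, so groups could separate by the wrong amount. Nor is it carried into section 4.1.
- **The methods use individual data.** Section 2.2 derives change from measurements before and after training, so a strictly constant prediction is an extreme case. It marks the end of a range and is not a forecast.
- **Silence is not exclusion.** For 1RM and H:Q ratio the factors are simply unstated, and the HMF paragraph defers to methods in cited work that the document does not reproduce. Group might be added in practice, but the plan does not commit to it.
- **No pass rule is written.** That a non-significant difference would be read as accuracy is an inference. It is a reasonable one, since section 4.1 cites earlier non-significant differences when setting out what it expects.

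**Conclusion.** The point holds as an omission with consequences: no analysis in the plan gives prediction error by training group or a method-by-group term, although the question is prediction of change from training volume. A pooled or by-sex mean difference cannot separate a correct method from one that pulls predictions toward the average change. In the illustrated extreme, detection is about 2% for the pooled test and about 89% for the group term (55% to 99% for SD 30 to 15 kg). These sizes rest on the assumed gains, on an error SD borrowed from 1RM levels, and on predictions centred on the average. They concern strength only, as the documents give no change or SD for CSA.

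The documents do not show that the study's methods behave this way, that every training-blind method would pass, or that training group is absent from the plan altogether.

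**What to change.** In section 4.1:

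1. Add training group as a between-subject factor, and the method-by-group interaction, to the accuracy analyses of change in 1RM, H:Q ratio and CSA. Keep the pooled comparison alongside.
2. Report the mean error of change with its 95% CI in each training group.
3. Report the slope of reference change on predicted change with its 95% CI.
4. Base the statement on accuracy on these estimates and intervals, not on a non-significant pooled difference and not on non-significance within groups of 12.

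The cost is SAP wording and a little more analysis; the data and groups are already planned. The drawback is wide intervals with 12 per group (about ±12.8 kg under the assumed SD), which should be reported as they are.
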